3 STATISTICAL METHODOLOGY

3.1 General Considerations

3.1.1 *Analysis Day*

Analysis day will be calculated from the date of first dose of study drug. The day of the first dose of study drug will be Day 1, and the day immediately before Day 1 will be Day -1. There will be no Day 0.

3.1.2 *Definition of Baseline*

Baseline is defined as the last measurement prior to the first dose of study drug.

3.1.3 *Visit Windows*

No analysis visit windows will be defined for this study, i.e., the nominal visits /time-points will be used for all statistical summaries/analyses.

3.1.4 *Summary Statistics*

Categorical data will generally be summarized with counts and percentages of subjects. The denominator used for the percentage calculation will be clearly defined. Continuous data will generally be summarized with descriptive statistics including n (number of non-missing values), mean, median, standard deviation, minimum, and maximum.

Summaries of change from baseline variables will include only patients who have both a baseline value and corresponding value at the post-baseline time point of interest.

3.1.5 *Hypothesis Testing*

All statistical comparisons will be made using two-sided tests at $\alpha = 0.05$. All null hypotheses will be of no treatment difference, and all alternative hypotheses will be two-sided. Confidence intervals will be two-sided, unless stated otherwise.

3.1.6 *Handling of Dropouts and Missing Data*

For all efficacy endpoints that do not include death as a possible outcome, data from subjects who die prior to Day 28 will be imputed at Day 28 based on the worst outcome. Other missing data for selected endpoints will be imputed using the methods as described in Section 3.4.

In cases of missing or incomplete dates (e.g. AE and concomitant medications), the missing component(s) will be assumed as the most conservative value possible. For example, AEs with missing start dates, but with stop dates either overlapping into the treatment period or missing,

will be counted as treatment-emergent, taking the worst-case approach. When partial dates are present in the data, both a partial start date and/or a partial stop date will be evaluated to determine whether it can be conclusively established that the AE started prior to the start of study drug or ended prior to the start of study drug. If the above cannot be conclusively established based on the partial and/or present dates, then the AE will be considered as treatment-emergent.

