3.4 Efficacy Assessment

All efficacy analysis will be performed using the ITT Population. Selected endpoints will be repeated on the FA and PP Populations. In addition, the efficacy analyses will be analyzed for pooled razuprotafib doses and placebo.

Additional analyses to understand safety and efficacy variables further may be carried out and will be labeled as post-hoc analyses.

3.4.1 *Efficacy Endpoints*

The following parameters will be analyzed using Cochran-Mantel-Haenszel (CMH) test stratified by disease severity:

- Proportion of subjects alive and free of respiratory failure at Day 28;
- Proportion of subjects alive and free of respiratory failure at Day 7;

All results will be summarized descriptively by treatment arm and expressed as proportions, along with corresponding 95% CI of the difference between response rates, and p-values. The 95% CI will be constructed using the normal approximation method.

Additional Analysis may be considered by incorporating other covariate adjustments into the analysis.

Respiratory failure will be defined as subjects who are on invasive mechanical ventilation; are receiving oxygen delivered by high-flow nasal cannula (heated, humidified, oxygen delivered via reinforced nasal cannula at flow rates >20 L/min with fraction of delivered oxygen ≥ 0.5) noninvasive positive pressure ventilation or extracorporeal membrane oxygenation; or have a

clinical diagnosis of respiratory failure (ie, clinical need for 1 of the preceding therapies, but preceding therapies not able to be administered in setting of resource limitation). Subject who die prior to the study timepoint (Day 7 or Day 28) will be imputed based on the worst outcome. Other missing responses will be imputed using a multiple imputation (MI) method under the assumption of missing at random (MAR).

Sensitivity Analysis

- All missing responses will be considered as non-responders and which will be imputed taking the worst case approach.
- The analysis will be repeated on FA and PP Populations.

The following parameters will be analyzed using the CMH test as stated above:

- Proportion of subjects alive and not requiring invasive mechanical ventilation at any time through Day 28;
- Proportion of subjects who improve by ≥ 2 categories on the NIAID 8-point ordinal scale from baseline to Day 7 and baseline to Day 28;
- Proportion of subjects who worsen by ≥ 2 categories on the NIAID 8-point ordinal scale from baseline to Day 7 and baseline to Day 28;

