- All-cause mortality at Day 7 and Day 28; and
- Proportion of subjects who were discharged and remained free of respiratory failure prior to Day 7 and Day 28.

The following parameters will be analyzed using an analysis of variance (ANOVA) model with effects for treatment, baseline value and disease severity as factors:

- Change in $\text{PaO}_2:\text{FiO}_2$ ratio from baseline to Day 7 (or discharge) and baseline to Day 28 (or discharge),
- Length of hospitalization and not requiring invasive mechanical ventilation from baseline to Day 7 and baseline to Day 28 or death,
- Length of hospitalization from baseline to Day 7 and baseline to Day 28 or death,

Missing responses will be imputed using a multiple imputation (MI) method under the assumption of missing at random (MAR).

All results will be summarized descriptively by treatment group, along with corresponding 95% CI of the difference between razuprotafib groups vs. placebo, and p-value.

The length of hospitalization will include all days that the subject is admitted to the hospital. For subjects who are discharged and readmitted to the hospital, the length of hospitalization will include the days after readmission.

Hospitalization days will be counted in 24-hour periods; any partial days will be counted as a whole day.

Days that subjects are on the ventilator will be counted as days of respiratory failure. Days that subjects are of respiratory failure based on the definition will be counted as days of respiratory failure. For subjects receiving high flow oxygen by a nasal cannula or noninvasive positive

pressure ventilation when enrolled, the length of respiratory failure will include all the days of respiratory failure from baseline.

The time-to-event endpoint of time to reach grade 6, 7 or 8 on the NIAID 8-point ordinal scale will be summarized descriptively using the Kaplan-Meier method. The Kaplan-Meier estimate of the median time as well as the 2-sided 95% confidence interval will be presented by treatment group.

The endpoint of number of subjects in each category of the NIAID 8-point ordinal scale at Day 7 and Day 28 will be summarized by treatment group and timepoint using descriptive statistics.

The endpoint of time to return to prehospitalization oxygen requirement will be summarized by treatment group using descriptive statistics.

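### Length of hospitalization has no clear rule for scoring deaths: none at Day 7, and one at Day 28 that can be read either way

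*SAP*

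**What the plan says.** SAP 3.4.1 lists "Length of hospitalization from baseline to Day 7 and baseline to Day 28 or death" among the endpoints governed by this sentence: "The following parameters will be analyzed using an analysis of variance (ANOVA) model with effects for treatment, baseline value and disease severity as factors". Results are reported "along with corresponding 95% CI of the difference between razuprotafib groups vs. placebo, and p-value". The counting rule, which also appears in Protocol 7.1, is "The length of hospitalization will include all days that the subject is admitted to the hospital". The only missing-data rule in that block is "Missing responses will be imputed using a multiple imputation (MI) method under the assumption of missing at random (MAR"), and it does not mention death.

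The general rule for deaths is in SAP 3.1.6 and Protocol 9.2.1. Its scope is "For all efficacy endpoints that do not include death as a possible outcome", and its action is that "data from subjects who die prior to Day 28 will be imputed at Day 28 based on the worst outcome". A second death rule, which does name both timepoints, is "Subject who die prior to the study timepoint (Day 7 or Day 28) will be imputed based on the worst outcome". It sits in the part of SAP 3.4.1 that defines respiratory failure and is not repeated for the ANOVA endpoints.

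This point is confined to the plain length of stay, where fewer days is the better result.

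**The concern.** A count of admitted days ends when the subject dies. A subject who dies on Day 4 and one sent home well on Day 4 (and not readmitted) therefore both score about 4 days, and on this endpoint that is a good score. A treatment arm with more early deaths could show a shorter mean stay, with a confidence interval and p-value attached.

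A worst-outcome rule would prevent this, but the SAP does not say whether its rule covers an endpoint with death in its own definition. Two programmers following the same SAP could derive different values for every subject who dies. Under some patterns of mortality, their treatment differences would have opposite signs.

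**Working it through.** **1. Which death rule reaches this endpoint?**

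| Rule | Day 7 version | Day 28 version |
|---|---|---|
| Count of admitted days (SAP 3.4.1) | Applies; ends at death | Applies; ends at death |
| Worst outcome (SAP 3.1.6, Protocol 9.2.1) | Not reached: acts only at Day 28 | Unclear: depends on whether this endpoint includes death; no worst value given |
| Worst outcome at Day 7 or Day 28 (SAP 3.4.1) | Written for the respiratory-failure endpoints | Same |
| MI under MAR (SAP 3.4.1, ANOVA endpoints) | Silent on death | Silent on death |

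SAP section 6, which lists changes from the protocol, does not settle the matter.

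**2. Size at Day 28.** The documents give no figure to reproduce: SAP 2.2.4 says no formal sample-size assessment was made, and no mortality or stay is stated. All of the following are therefore assumptions: mortality m of 20% (active) and 10% (placebo), survivors' mean stay S = 12 days, mean day of death D varied from 5 to 16, no other difference between arms, and a worst value of 28 days.

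- Counted to death: mean stay = (1 − m)S + mD, so the difference (active minus placebo) = (0.20 − 0.10)(D − S).
- Deaths scored 28: mean stay = (1 − m)S + 28m, so the difference = (0.20 − 0.10)(28 − S).

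| D | Active, to death | Placebo, to death | Difference, to death | Difference, deaths = 28 |
|---|---|---|---|---|
| 5 | 0.8×12 + 0.2×5 = 10.6 | 0.9×12 + 0.1×5 = 11.3 | −0.7 | +1.6 |
| 9 | 9.6 + 1.8 = 11.4 | 10.8 + 0.9 = 11.7 | −0.3 | +1.6 |
| 12 | 9.6 + 2.4 = 12.0 | 10.8 + 1.2 = 12.0 | 0.0 | +1.6 |
| 16 | 9.6 + 3.2 = 12.8 | 10.8 + 1.6 = 12.4 | +0.4 | +1.6 |

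The last column is 15.2 − 13.6 (0.8×12 + 0.2×28 against 0.9×12 + 0.1×28) and does not depend on D. For S from 10 to 14 days it runs from +1.8 to +1.4. Over the same range the to-death difference at D = 5 runs from −0.5 to −0.9, and at D = 16 from +0.6 to +0.2.

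**3. Size at Day 7.** Assume 10% v 2% mortality by Day 7, a survivors' mean of 6 to 6.5 days within the window, and death on Day 3 to 5. The to-death difference is 0.08 × (D − S): from 0.08 × (5 − 6) = −0.08 to 0.08 × (3 − 6.5) = −0.28 days. Scoring deaths as 7 days gives +0.08 (S = 6) or +0.04 (S = 6.5).

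**4. Effect on the test.** The simulation used 4,000 trials of 40 v 40, which is Part 2 at 1:1:1 (120/3). Survivors' stays were gamma (shape 3, mean 12), rounded up and capped at 28. Death days were uniform over the stated range, and mortality was higher in the severe stratum. The model was linear, with treatment and severity, at two-sided 0.05.

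| Mortality; death days | To death: mean difference | To death: significantly shorter | Deaths = 28: mean difference | Deaths = 28: significantly shorter |
|---|---|---|---|---|
| 10% v 10%; 2–12 | 0.0 | 2.2% | 0.0 | 2.1% |
| 20% v 10%; 2–12 | −0.5 | 5.9% | +1.6 | 0.2% |
| 30% v 10%; 2–12 | −1.1 | 11.4% | +3.1 | 0.0% |
| 20% v 10%; 2–26 | +0.2 | 1.9% | +1.6 | 0.4% |

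When deaths are spread over days 2–26 the false advantage disappears, but the to-death count still shows only +0.2 days where the worst-value count shows +1.6.

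**The case against.** A reader might infer that the plan settles on scoring death as a short stay, and so that an arm with more deaths will look better. The documents do not support that.

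First, SAP 3.1.6 can fairly be read to cover the Day 28 version. Some endpoints plainly include death as an outcome: alive and free of respiratory failure, all-cause mortality, and the NIAID scale with death as grade 1. A length of stay is a number of days, and the mention of death may only mark where counting ends. On that reading the worst-outcome rule applies and the Day 28 problem is reversed. A raw count with a general imputation rule laid over it is normal practice, so it is also too strong to call the two passages contradictory.

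Second, the false advantage requires deaths that come, on average, before the survivors' mean stay. It is gone when the two coincide and reverses after that. The chance of a significant result in the wrong direction is modest at 20% v 10%: 5.9% against 2.2% with equal mortality, and that with all deaths by Day 12.

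Third, this is one of 13 efficacy endpoints in SAP 2.3.1, and none is named primary. All-cause mortality at both timepoints is tested in the same section, so excess deaths would be visible beside any shorter stay.

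All three points stand, and they limit the finding. They do not supply a death rule at Day 7, a numeric worst value, or a statement of which reading holds at Day 28.

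**Conclusion.** The concern holds as a gap in specification. At Day 7 the stated counting rule scores an early death as a short stay, and no other rule clearly corrects it. At Day 28 the same happens on one reasonable reading; on the other, death is penalised by a value the SAP never gives.

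Under the assumed 20% v 10% mortality and 12-day survivors' stay, the choice of reading moves the estimated difference from between −0.7 and +0.4 days to +1.6 days. The literal count rewards deaths that come earlier than the survivors' mean stay and understates harm when they come later. The direction under the literal count depends on the timing of death, which the documents do not give. It would be wrong to say that the plan generally favours the arm with more deaths. Severity: should-fix.

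**What to change.** In SAP 2.3.1 and 3.4.1, remove death as a point at which counting stops. State that any subject dead by Day 7 or by Day 28, wherever the death occurred, is scored at the worst value for that window: 7 or 28 days, or equivalently 0 days alive and out of hospital. State also that this governs over SAP 3.1.6 and over multiple imputation. Deleting the reference to death is not enough by itself, because a count of admitted days ends at death anyway; the explicit score is what matters. Record the change in SAP section 6.

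The protocol's ANOVA can stay. A severity-stratified rank test (van Elteren) is a reasonable optional sensitivity analysis, since deaths will pile up at one value, but the defect does not require it.

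The cost is SAP wording and a small derivation change. The admission, discharge and death data are already needed for the existing endpoints. The downside is that the endpoint becomes a composite of stay and death, in which a death ties with a subject in hospital for the whole window, so it should be labelled as such and read beside mortality.

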In addition to the routine clinical monitoring that is part of standard of care, the following will be conducted: vital signs, blood chemistry, hematology, and coagulation will be assessed during the Treatment Period and until Day 28, unless discharged; 12-lead electrocardiograms will be performed at Screening, on Day 7 (or at discharge if subject is discharged prior to Day 7), and on the last day of dosing if the study drug dosing duration is increased to up to 14 days; data on the subject's oxygen support requirements (ie, peripheral capillary oxygen saturation [SpO_2]:fractional inspired oxygen [FiO_2] ratio or partial pressure of oxygen [PaO_2]: FiO_2 ratio if arterial blood gas is being performed per standard of care) will be collected during the Treatment Period and until Day 28, unless discharged; clinical status based on the National Institute of Allergy and Infectious Diseases (NIAID) 8-point ordinal scale and AEs will be assessed through Day 28; blood sampling for PK analysis will occur on Day 1 and Day 6 for Part 1 and may occur for Part 2; and blood sampling for biomarkers associated with coagulation, inflammation, and vascular leakage (CRP and D-dimer assessed at local laboratory; Angpt-2, IL-6, IL-8, TNF α , and HMGB-1 assessed at central laboratory) will occur at Screening and on Day 7 (or at discharge if subject is discharged prior to Day 7) for all subjects. If the study drug dosing duration is increased to up to 14 days, blood sampling for biomarkers will also occur on the last day of dosing. For all subjects remaining hospitalized on Day 14 or beyond, blood sampling for biomarkers will also occur on Day 28 or the day of hospital discharge, whichever occurs first.

The duration of the study for each subject will be approximately 29 days: Screening (approximately 1 day), Treatment Period (7 days [or up to 14 days if recommended by the DRC]), and Post-Treatment Observation Period (approximately 21 days [or 14 to 20 days if Treatment Period is extended]).

The study will take place at approximately 20 sites in the United States.

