8.8 Clinical Laboratory Evaluations

Samples for blood chemistry, hematology, and coagulation will be obtained as indicated in [Appendix A](#). See [Appendix B](#) for a complete list of analytes. If a blood chemistry, hematology, or coagulation assessment was performed within 24 hours prior to the first dose of study drug, it is not necessary to repeat the assessment on Day 1. Effort should be made to obtain blood chemistry, hematology, and coagulation at approximately the same time on each day indicated in [Appendix A](#); however, it should not be considered a protocol deviation if this is not possible. After the Treatment Period, blood chemistry, hematology, and coagulation will be assessed weekly until Day 28, unless discharged. All safety clinical laboratory evaluations will be performed at the local laboratory as indicated in [Appendix A](#).

A local urine pregnancy test will be performed for females of childbearing potential only at Screening.

Arterial blood gas should be obtained locally only if clinically indicated. If arterial blood gas is obtained, the subject's current oxygen requirement should also be recorded.

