2.3 Study Endpoints

2.3.1 *Efficacy Endpoints*

The efficacy endpoints include the following:

- Proportion of subjects alive and free of respiratory failure at Day 28;
- Proportion of subjects alive and free of respiratory failure at Day 7;
- Proportion of subjects alive and not requiring invasive mechanical ventilation at any time through Day 28;
- Time to reach grade 6, 7 or 8 on the NIAID 8-point ordinal scale;
- Change in PaO₂:FiO₂ ratio from baseline to Day 7 (or discharge) and baseline to Day 28 (or discharge);

- Length of hospitalization and not requiring invasive mechanical ventilation from baseline to Day 7 and baseline to Day 28 or death;
- Length of hospitalization from baseline to Day 7 and baseline to Day 28 or death;
- Proportion of subjects who improve by ≥ 2 categories on the National Institute of Allergy and Infectious Diseases (NIAID) 8-point ordinal scale from baseline to Day 7 and baseline to Day 28;
- Proportion of subjects who worsen by ≥ 2 categories on the NIAID 8-point ordinal scale from baseline to Day 7 and baseline to Day 28;
- All-cause mortality at Day 7 and Day 28;
- Number of subjects in each category of the NIAID 8-point ordinal scale at Day 7 and Day 28;
- Time to return to prehospitalization oxygen requirement; and
- Proportion of subjects who were discharged and remained free of respiratory failure prior to Day 7 and Day 28.

The NIAID 8-point ordinal scale includes the following grades:

1. Death;
2. Hospitalized, on invasive mechanical ventilation or Extracorporeal membrane oxygenation (ECMO);
3. Hospitalized, on noninvasive ventilation or high-flow oxygen devices;
4. Hospitalized, requiring supplemental oxygen;
5. Hospitalized, not requiring supplementation oxygen – requiring ongoing medical care (COVID-19 related or otherwise);
6. Hospitalized, not requiring supplemental oxygen – no longer requires ongoing medical care;
7. Not hospitalized, limitation on activities and/or requiring home oxygen; and
8. Not hospitalized, no limitations on activities.

2.3.2 *Pharmacodynamic (PD) and Pharmacokinetic (PK) endpoints*

The PD and PK endpoints include in the following:

- Change from baseline in CRP and D-dimer;
- Change from baseline in systemic biomarkers of vascular leakage and inflammation (ie, Angpt-2, IL-6, IL-8, TNF α , and HMGB-1);
- Summary of plasma concentrations of biomarkers at each sampling time point for each treatment group; and

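### Change in PaO2:FiO2 rests on gases drawn only when clinically indicated; the SAP imputes gaps under MAR without providing for the scheduled NIAID and SpO2:FiO2 data, and gives no clear score for deaths before Day 7

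*SAP*

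**What the plan says.** **Endpoint.** SAP 2.3.1 lists the change in PaO2:FiO2 "ratio from baseline to Day 7 (or discharge) and baseline to Day 28 (or discharge"). SAP 3.4.1 analyses it by ANOVA with treatment, baseline value and disease severity, and reports a 95% interval and p-value.

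**Data.** Protocol 8.8: "Arterial blood gas should be obtained locally only if clinically indicated". Protocol 3.1.1 and Appendix A (footnote m) schedule SpO2:FiO2, or PaO2:FiO2 "if arterial blood gas is being performed per standard of care", three times daily on treatment and then daily until discharge. Footnote n schedules NIAID status at the same frequency for every inpatient.

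**Missing values.** For the ANOVA endpoints, SAP 3.4.1 says: "Missing responses will be imputed using a multiple imputation (MI) method under the assumption of missing at random (MAR"). It lists no imputation variables. The SpO2:FiO2 ratio appears nowhere in the SAP.

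**Deaths.** For endpoints that do not include death, SAP 3.1.6 and Protocol 9.2.1 say "data from subjects who die prior to Day 28 will be imputed at Day 28 based on the worst outcome". SAP 3.1.6 continues: "Other missing data for selected endpoints will be imputed using the methods as described in Section 3.4". In SAP 3.4.1, within the paragraph on the respiratory-failure proportions: "Subject who die prior to the study timepoint (Day 7 or Day 28) will be imputed based on the worst outcome". The ANOVA paragraph has no such sentence.

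**The concern.** A change score needs two gases, and the model also needs the baseline one. Protocol 4.1 admits moderate disease with no gas at all, and severe disease on respiratory rate, heart rate or SpO2 alone. For a subject discharged before Day 7, Appendix A (footnote c) moves the Day 7 procedures to the discharge day, when a gas is plausibly least likely. Missing values therefore follow from the design and are plausibly related to oxygenation.

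MAR is more credible when the clinical status that prompts a gas is in the imputation model. The protocol collects that status, but the SAP does not say that it is used. Nor does it say what happens when the baseline ratio is missing; its rule speaks of responses.

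Deaths are the sharper problem. Followed as written, a Day 5 death takes the worst outcome at Day 28 but a survivor-like value at Day 7. The Day 7 oxygenation comparison could then credit an arm for patients who died.

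**Working it through.** The plan gives no gas frequency, SD, effect size, power or death rate for this endpoint, so there is no figure to reproduce. Arm sizes are 30/3 = 10 in each step of Part 1 and 120/3 = 40 in Part 2 (80 and 40 if randomized 2:1). **All other inputs below are assumed.**

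**1. Which rule reaches a death before Day 7?**
- SAP 3.1.6 and Protocol 9.2.1 give a worst outcome, but only at Day 28.
- The SAP 3.4.1 sentence naming Day 7 is in the respiratory-failure paragraph.
- The SAP 3.4.1 ANOVA paragraph prescribes MAR imputation with no exception for deaths.

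No sentence clearly gives a Day 7 score for PaO2:FiO2. The worst outcome has no value for a change in ratio at either timepoint.

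**2. Share of change scores missing.** With gas rates p0 at baseline and p1 at follow-up, independent, the share is 1 - p0 × p1.
- 95% and 95%: 1 - 0.95 × 0.95 = 9.8%.
- 20% and 20%: 1 - 0.20 × 0.20 = 96%. If the same subjects have both gases, this falls to 1 - 0.20 = 80%.

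**3. What the scheduled data add.** Simulated Part 2, 80 active against 40 placebo, half moderate:
- Baseline ratio N(340, 60) moderate, N(200, 60) severe.
- Day 7 = baseline + 60 + effect - 0.3 × (baseline - 270) + N(0, 90), clipped to 40-650.
- Effect 40 in all, or 80 in severe and 0 in moderate.
- SpO2:FiO2 = PaO2:FiO2 plus noise of SD 60 or 120, capped at 476.
- NIAID as four levels of PaO2:FiO2 plus independent noise of the same SD.
- Gas ordering rises as SpO2:FiO2 or PaO2:FiO2 falls.
- 20 imputations, 24 cells, 500 runs each. The complete-data 95% interval is about ±35 around an effect of about 40.

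RMSE relative to complete data:

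| Imputation variables | about 10% missing | about 50% | about 73% |
|---|---|---|---|
| ANOVA's own | 0.98-1.03 | 1.18-1.33 | 1.44-1.63 |
| plus NIAID | 0.98-1.03 | 1.09-1.27 | 1.17-1.42 |
| plus NIAID and SpO2:FiO2, never recorded with a gas | not run | 1.07-1.25 | 1.17-1.42 |
| plus NIAID and SpO2:FiO2 in everyone (upper bound) | no material gain | 1.01-1.24 | 1.06-1.39 |

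Cell by cell, RMSE falls by 5-16% (50% missing) and 5-19% (73%) under either/or recording, and by 6-19% and 11-30% at the upper bound. Each RMSE alone carries about 3% Monte Carlo error (1/√(2 × 500)), less in paired comparisons.

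Bias with the ANOVA's own variables is -6% to +1%, -22% to +3% and -28% to +1% at the three levels. With NIAID and either/or SpO2:FiO2 it is -22% to +1% and -29% to -3% at the last two.

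A separate large-sample run (200,000 per arm) assumed complete baselines, SpO2:FiO2 in everyone and gas ordering driven by it alone, so MAR held by construction. A true difference of 30 came back as 28.8-30.6 with SpO2:FiO2 in the model and 21.7-28.8 without. With no true effect, both models stayed within 0.8 units of zero.

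**4. Deaths.** Assume a survivor mean change of +60 and a worst change near -150 (for example a follow-up ratio of 50 from the assumed severe mean of 200: 50 - 200 = -150). The gap is 60 + 150 = 210.
- One death in 40: 210/40 = 5.25 units.
- One death in 10: 210/10 = 21 units.
- Imbalance of 5 points (2 of 40): 0.05 × 210 = 10.5 units, or 10.5/35 = 30% of the interval's half-width.
- Balanced deaths: 0.

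**The case against.** **SAP 3.1.6 may already keep MAR away from deaths.** Its sentence on other missing data follows the death rule, so the word other can mean data not from decedents. That reading is fair, but it still supplies no Day 7 score. The Day 7 sentence in 3.4.1 may also have been meant for the whole section; the text does not say so.

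**Deaths are not hidden.** Mortality and being alive and free of respiratory failure are both tested at Day 7. This stands and limits the harm, but does not correct the oxygenation comparison.

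**Imputation variables belong in the programming specifications.** SAP 7 places those in a separate document, which may name them. Missing detail alone would be a small matter. How deaths count and which scheduled data support MAR are analysis choices that belong in the SAP.

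**SpO2:FiO2 adds little.** This stands. If it is seldom recorded with a gas, nearly all the gain comes from NIAID. The simulation builds NIAID from PaO2:FiO2, whereas real grades follow oxygen device, need for care and hospital status, so even that gain is assumed.

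**A much larger death effect could be drawn.** A reader might take a worst change of -290. From a severe baseline of N(200, 60) that gives a negative ratio for every baseline below 290, about 93% of severe subjects. Even a uniform -150 falls below the simulated floor of 40 for about 43% of them. The worst outcome should therefore be set on the ratio, not on the change.

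**Conclusion.** The point holds as a should-fix, with medium confidence. The dependence on gases drawn for clinical reasons and the lack of a clear Day 7 death score for this endpoint both follow from the text. The sizes do not: they rest on assumed gas rates, variances, survivor means and worst values.

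Three stronger inferences are not supported:
- **That MAR is wrong in itself.** It can be reasonable given the status that prompts a gas; the gap is that the SAP does not provide for using that status.
- **That adding the scheduled data cures bias.** It did so only where MAR held by construction and SpO2:FiO2 was known for everyone. Otherwise the gain was in precision, and nothing material at 10% missing.
- **That the rule creates a false benefit.** With no true effect, neither imputation model showed appreciable bias in the difference, although that run contained no deaths. Misplaced death scores move the difference only when deaths are unbalanced.

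This is one of 13 listed efficacy endpoints, with none labelled primary and no power stated. The issue is whether this endpoint can be interpreted, not the validity of a powered test.

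**What to change.** In SAP 3.4.1, for change in PaO2:FiO2:

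1. **Deaths.** State that a death before the timepoint analysed (Day 7 or Day 28) receives the worst outcome, and limit MAR imputation of follow-up values to subjects alive at that timepoint. Define the worst outcome on the follow-up ratio, for example the lowest follow-up ratio observed in any subject, fixed blinded before lock. Derive the change from each subject's own baseline, so that no negative ratio is implied. Assign this score after imputation, so that it does not enter the imputation model.
2. **Imputation model.** Include treatment, severity, serial NIAID status and, where recorded, SpO2:FiO2. Impute missing baseline ratios for all subjects, including those who die.
3. **Reporting.** Show by arm how many subjects have both gases, and report change in SpO2:FiO2 as a supportive analysis. A delta-adjusted analysis is optional.

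**Cost.** SAP wording and some programming before lock; no protocol change. SpO2:FiO2 has a ceiling: on room air (FiO2 0.21 assumed), 93% to 100% spans only 93/0.21 = 443 to 100/0.21 = 476, or 33 units. It may be absent in ventilated subjects, because Protocol 8.9 collects vital-sign SpO2 only in the non-ventilated. Protocol 8.8 says that with a gas the "current oxygen requirement should also be recorded", but not that this means FiO2. A lowest observed ratio can also hinge on one extreme value.
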